11 ADVERSE EVENTS / ADVERSE REACTIONS

11.1 Definitions – Device Adverse Events

Adverse Event (AE): An AE is any untoward medical occurrence in a subject administered the CTM, which does not necessarily have a causal relationship with the treatment. An AE can therefore be any unfavorable and unintended sign, (including an abnormal laboratory finding) symptom or disease temporally associated with the use of the CTM, whether or not related to the CTM.

Adverse Device Effect (ADE): An AE related to the use of an investigational medical device.

NOTE 1: This definition includes Adverse Events resulting from insufficient or inadequate instructions for use, deployment, implantation, installation, or operation, or any malfunction of the investigational medical device.

NOTE 2: This definition includes any event resulting from use error or from intentional misuse of the investigational medical device.

Anticipated Serious Adverse Device Effect: An effect which by its nature, incidence, severity or outcome has been identified in the Investigator Brochure.

Serious Adverse Event (SAE): Any untoward medical occurrence that:

- Results in death;
- Is life-threatening ("Life-threatening" refers to an event in which the subject was at risk of death at the time of the event. It does not refer to an event which hypothetically might have caused death if it were more severe.);
- Requires inpatient hospitalization or prolongation of existing hospitalization;
- Results in persistent or significant disability/incapacity;
- Is a congenital anomaly/birth defect;
- Required intervention to prevent permanent impairment or damage.

Serious Adverse Device Effect (SADE): An ADE that has resulted in any of the consequences characteristic of a serious adverse event.

Unanticipated Serious Adverse Device Event: An SAE effect which by its nature, incidence, severity or outcome has not been identified in the current version of the Investigator's Brochure.

11.2 Definitions – Drug Adverse Events

Adverse Event (AE): An adverse event (sometimes referred to as an adverse experience) means any untoward medical occurrence associated with the use of a drug in humans, whether or not considered drug related.

Suspected Adverse Reaction (SAR): A suspected adverse reaction means any adverse event for which there is a reasonable possibility that the drug caused the event.

Adverse Reaction (AR): An adverse reaction means any adverse event caused by a drug. Adverse reactions are a subset of all suspected adverse reactions where there is reason to conclude that the drug caused the event.

Unexpected AE/SAR/AR: An adverse event, suspected adverse reaction or adverse reaction is considered “unexpected” if it not listed in the Investigator Brochure.

Serious AE/SAR/AR: An adverse event, suspected adverse reaction or adverse reaction is considered “serious” if, in the view of either the investigator or sponsor, it results in death, a life-threatening adverse event, inpatient hospitalization or prolongation of existing hospitalization, a persistent or significant incapacity or substantial disruption of the ability to conduct normal life functions, or a congenital anomaly/birth defect. If either the investigator or sponsor believes that an event is serious, the event will be considered serious and evaluated by the sponsor for expedited reporting.

Suspected Unexpected Serious Adverse Reaction (SUSAR): An adverse event, suspected adverse reaction or adverse reaction is considered a SUSAR if it meets the criteria of both “Unexpected” and “Serious” as defined in this section. Any event believed to be a SUSAR by the investigator and/or the sponsor will be evaluated by the sponsor for expedited reporting.

11.3 Relationship

The Relationship between an AE and the CTM will be determined by the Investigator on the basis of his or her clinical judgment and the following definitions:

Definitely Related: The AE follows a reasonable temporal sequence from administration of the CTM; the AE follows a known or expected response pattern to the CTM.

Probably Related: The AE follows a reasonable temporal sequence from administration of the CTM; the AE follows a known or expected response pattern to the CTM; and the AE could not be reasonably explained by the known characteristics of the subject's clinical state.

Possibly Related: The AE follows a reasonable temporal sequence from administration of the CTM; the AE follows a known or expected response pattern to the CTM, but could readily have been produced by a number of other factors.

Unlikely Related: The AE which etiology is unlikely related to the CTM even if event may follow a known or expected response pattern to the CTM, and likely to be produced by a number of other factors. Sufficient information is not available at the time of the AE to determine its causality.

Not Related: An AE for which sufficient information exists to indicate that the etiology is unrelated to the CTM. One or more of the following variables apply:

- The AE does not follow a reasonable temporal sequence following administration of the CTM;
- The AE is readily explained by the subject's clinical state or other therapies.

For events that are determined to be definitely, probably or possibly related, additional information on the relationship and timing of the event in relation to the arthrocentesis and study injection will be captured.

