11.5.5 Study Discontinuation

Enrollment will be suspended if a subject experiences a serious and/or life-threatening AE that is probably or definitely related to the study injection. The study will be stopped if in the opinion of the PI, medical monitor, and Sponsor that the safety of subjects is uncertain. The decision to resume enrollment, permanently discontinue the trial, or otherwise modify the study will be made by the Medical Monitor in consultation with the IDMC. Additionally, the triggering of the stopping rules will prompt notification to the appropriate regulatory agencies including the Competent Authorities and the ECs.

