12.4 Adverse Events

All AEs will be coded according to MedDRA. Safety assessments will include Treatment-Emergent Adverse Events (TEAEs) which are defined as AEs with an Investigator assessment of definitely, probably, or possibly related to CTM. TEAEs will be summarized with frequencies and percentages by system organ class and preferred term, severity, and relationship to study CTM for each treatment group. In summaries of TEAEs by severity and relationship to CTM for subjects reporting multiple episodes, all reported events will be included, not only the worst reported case. Serious Adverse Events will also be presented by relationship to the CTM.

The number of subjects with at least one AE will be tabulated for each treatment group. Differences between the treatment groups will be tested using Fisher's exact test. Then the number of AEs for each treatment group will also be tabulated.

The number of subjects and the number of AEs will be tabulated by severity, relationship, and local injection site specific events versus non local events.

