14.2.2 Anticipated Adverse Reactions

Reported adverse reactions associated with the IA use of hyaluronic acid:

Intra-articular injection of sodium hyaluronate preparations has occasionally been associated with allergic/anaphylactic reactions and transient hypotension, which have generally resolved spontaneously or after conservative treatment.

The most common reported adverse events associated with Monovisc are the following: arthralgia, joint swelling and injection site pain.

Incidences of rash, headache, dizziness, chills, hives, itching, nausea, muscle cramps, peripheral edema, and malaise have also been reported in association with intra-articular injections.

A study conducted by Anika Therapeutics, Inc. on Monovisc recorded information on AEs that were possibly, probably and definitely related to the study injection. Patients who received Monovisc had 7.1% of AEs related to the study injection and 5.4% of patients who received saline had an AE related to the study injection. Most of the AEs were minor complications that required little or no treatment. These included injection site events, joint swelling, joint pain, and limb pain. The rate of joint pain and limb pain not related to the study injection was higher than the rate related to the study injection [26].

Reported adverse reactions associated with the IA use of corticosteroids:

Dermatologic: Whitening of the skin at the injection site, local fat atrophy.

Musculoskeletal: Joint infection, joint swelling and pain several hours after injection, tendon rupture, pain, swelling, ligament damage.

Neurological: Nerve damage.

General: Infection, local bleeding, allergic reactions.

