- Anika Therapeutics, Inc. will verify that each subject has consented, in writing, to direct access to his/her original medical records for trial-related monitoring, audit, EC review, and regulatory inspection.
- Anika Therapeutics, Inc. is responsible for the ongoing safety evaluation of the CTM.
- Anika Therapeutics, Inc. will notify all concerned Investigators/institutions and the regulatory authority(ies) of findings that could affect adversely the safety of subjects, impact the conduct of the trial, or alter the EC approval/favorable opinion to continue the trial.

- Anika Therapeutics, Inc. will submit any required application(s) to the appropriate authority(ies) for review, acceptance, and/or permission (as required by the applicable regulatory requirement(s)) to begin the trial(s).
- Anika Therapeutics, Inc. will ensure that all required EC, or other regulatory approvals are obtained and documented; and that appropriate provisions are made to meet any specific conditions imposed by the EC. Anika will ensure that any modification(s) required by the EC or other regulatory authority are made and documented by the PI and have gained the approval of the EC or other regulatory authority.
- Anika Therapeutics, Inc. will expedite the reporting to all concerned Investigator(s)/institutions(s), to the EC, where required, and to the regulatory authority(ies) of all ADEs that are both serious and unexpected.
- Anika Therapeutics, Inc. will submit to the regulatory authority(ies) all safety updates and periodic reports, as required by applicable regulatory requirement(s).
- Anika Therapeutics, Inc. will ensure that an ongoing risk analysis, based on existing knowledge of the type of product and its intended use, is performed and provided to the Investigator involved in a clinical study with the CTM, through the Investigator's Brochure or updates to it and to the subject through the ICF or updates to it.
- Anika Therapeutics, Inc. will also incorporate the risk analysis and risk management plan of the CTM and share this with the Investigators;
- Anika Therapeutics, Inc. shall be responsible for:
 - Documenting correspondence with all parties involved in the clinical study, including the EC and regulatory authorities;
 - Ensuring that the clinical study is appropriately monitored by determining the extent and nature of the monitoring;
 - Reviewing the monitoring reports and follow-up on actions required in the monitoring report;

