4.4 ADVERSE EVENTS

All AEs will be coded according to MedDRA. Safety assessments will include Treatment-Emergent Adverse Events (TEAEs) which are defined as AEs with an Investigator assessment of definitely, probably, or possibly related to CTM. TEAEs will be summarized with frequencies and percentages by system organ class and preferred term, severity, and relationship to study CTM for each treatment group. In summaries of TEAEs by severity and relationship to CTM for subjects reporting multiple episodes, all reported events will be included, not only the worst reported case. Serious Adverse Events will also be presented by relationship to the CTM.

The number of subjects with at least one AE will be tabulated for each treatment group. Differences between the treatment groups will be tested using Fisher's exact test. Then the number of AEs for each treatment group will also be tabulated.

The number of subjects and the number of AEs will be tabulated by severity, relationship, and local injection site specific events versus non local events.

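### Every related grade in protocol 11.3 requires an already known or expected reaction pattern, so a new type of harm has no suitable causality grade and drops out of the TEAE summaries in all arms

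*Protocol*

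**What the plan says.** Protocol 11.3 has the Investigator grade each event using clinical judgment together with five definitions. The three related grades all contain the same pattern element, in addition to reasonable timing:

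- Definitely Related: "the AE follows a known or expected response pattern to the CTM".
- Probably Related: "the AE follows a known or expected response pattern to the CTM; and the AE could not be reasonably explained" by the subject's known clinical state.
- Possibly Related: "the AE follows a known or expected response pattern to the CTM, but could readily have been produced by a number of other factors".

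The same section collects further detail on relationship and timing only for events in these three grades.

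The grades then drive the safety analysis. Protocol 12.4 and SAP 4.4 count as TEAEs only those events "which are defined as AEs with an Investigator assessment of definitely, probably, or possibly related to CTM". SAP 4.4 adds: "TEAEs will be summarized with frequencies and percentages by system organ class and preferred term, severity, and relationship to study CTM for each treatment group". Protocol 11.5.5 suspends enrollment after a "serious and/or life-threatening AE that is probably or definitely related to the study injection".

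Elsewhere the protocol allows for reactions nobody has yet described. Section 11.2 defines a suspected adverse reaction by a reasonable possibility that the drug was the cause, with no pattern condition. It treats as unexpected anything not listed in the Investigator Brochure. Section 16.7 commits the sponsor to expedited reporting "of all ADEs that are both serious and unexpected", and 11.1 defines an ADE as an event related to use of the device.

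**The concern.** A causality scale should let the rater record that the study product may have caused something new. Here, novelty alone disqualifies an event from every related grade. The extension adds about 13 weeks of follow-up with safety as a stated objective, and a late, previously undescribed effect is one of the things such follow-up could show. If the rater applies the definitions as written, that effect is left out of the only safety summary planned by system organ class and preferred term. Events of this kind could also be graded differently from site to site, because no grade suits them.

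**Working it through.** There is no plan figure to reproduce. The check sets the definitions side by side and follows one event through them.

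**Step 1. Grade a test event.** Take an AE with reasonable timing, no alternative explanation, and no previous description for the product.

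| Grade in 11.3 | Timing element | Pattern element | Other-cause element | Result |
|---|---|---|---|---|
| Definitely | met | not met | none | fails |
| Probably | met | not met | met (no other explanation) | fails on pattern alone |
| Possibly | met | not met | not met (no competing factors) | fails |
| Unlikely | none | none | requires other likely causes; not met | poor fit |
| Not Related | would need implausible timing; not met | none | or a ready alternative explanation; not met | fails |

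The pattern element is present in 3 of 3 related grades, and none of the five grades clearly fits. Unlikely Related also mentions insufficient information at the time of the event, so a rater might place the event there. The rest of that definition still points to other causes.

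**Step 2. Does the word expected rescue it?** Section 11.2 makes an event unexpected when it is absent from the Investigator Brochure. On that meaning a previously undescribed harm is neither known nor expected, so the alternative wording does not help.

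**Step 3. Compare with the other sections.**

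- 11.2 needs only a reasonable possibility of causation, and its unexpected and SUSAR categories assume that an unlisted event can be a reaction. The test event can qualify under 11.2 and fail under 11.3.
- 16.7 requires an event to be related (through the ADE definition in 11.1) and also unexpected. Under 11.3 an event new in kind cannot be both. The category is not empty, however: 11.1 judges anticipation by nature, incidence, severity or outcome, so a familiar reaction of unusual severity can be related and still unanticipated. 16.7 therefore sits badly with 11.3 without flatly contradicting it.

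**Step 4. Follow the event into the outputs.**

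| Output | Test event included? |
|---|---|
| TEAE summaries by system organ class and preferred term (12.4, SAP 4.4) | no, in any arm |
| Extra relationship and timing data (11.3) | no |
| Suspension wording of 11.5.5, if serious | no |
| Recording on the eCRF (11.5.1) | yes |
| Subjects with at least one AE, Fisher's exact test (12.4, SAP 4.4) | yes |
| Counts by severity, relationship and local versus non-local (12.4, SAP 4.4) | yes, under whichever grade was chosen |
| 24-hour SAE report irrespective of relationship (11.5.2) | yes, if serious |
| SUSAR definition: unexpected plus serious (11.2) | yes, if serious |
| Sponsor evaluation for expedited reporting (11.5.3) | yes, if serious |

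**The case against.** The best defence is that this is a narrow wording conflict with several safeguards around it. Clinical judgment enters the rating, so an investigator may depart from the letter of the definitions. 11.3 does not itself say that expected means listed in the Brochure; that link comes from 11.2. Step 4 shows that recording, the any-AE comparison and serious-event reporting do not depend on the grade. Suspension is also a weak consequence, because 17-02 gives no injection and 11.5.5 separately allows the study to be stopped when safety is uncertain. Section 16.19 adds termination for unexpected or unacceptable risk.

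Most of this stands and limits the point. It does not remove it: 11.3 asks for judgment and the definitions together, and none of the safeguards returns the event to the TEAE summaries.

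A reader might go further and infer a bias against Cingal. It contains hyaluronate and a corticosteroid, and 14.2.2 has a hyaluronate list as well as one headed "Reported adverse reactions associated with the IA use of corticosteroids", so more events might look familiar after Cingal than after Monovisc or TH. The documents do not support that inference:

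- 11.3 never refers to 14.2.2, and 14.2.2 assigns no list to an arm. Part of its hyaluronate text speaks of intra-articular injections generally.
- The effect needs a rater who knows the arm. The PI is most often the unblinded Treating Physician, but the Blinded Evaluator collects and records the AEs.
- A narrower reaction profile for a product without steroid is partly sound causality assessment.
- No event frequencies by reaction type are given, so any inflation ratio would rest on an invented fraction.

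A reader might also infer that a new harm would simply be graded Unlikely Related, or would vanish. Neither follows. That grade requires other likely causes, and the event remains in the database and the any-AE comparison.

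**Conclusion.** The concern holds as a conflict between 11.2 and 11.3 with a defined, limited effect. On the literal reading, an event that is new in kind is excluded in every arm from the system-organ-class and preferred-term TEAE summaries and from the extra relationship and timing data, and, if serious, it does not meet the suspension wording of 11.5.5. Its other recording and reporting routes remain.

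This rests on two assumptions: raters apply the definitions as written, and expected carries the meaning implied by 11.2. The documents give no rate for undescribed reactions, so the number of events affected cannot be stated and may be zero. The conclusion needs no assumption about blinding, product-specific lists or event frequencies, and it makes no claim of a difference between arms. It merits correction because the wording is easily repaired and the affected summaries are the main coded display of safety.

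**What to change.** - **Protocol 11.3:** bring the scale into line with the reasonable-possibility standard of 11.2. A known or expected pattern should count as supporting evidence and not as a required element, at least for Possibly and Probably Related. Keeping it for Definitely Related would do little harm, since the lower related grades would then admit a new event to the TEAE summaries.
- **Expectedness:** assess it against the Investigator Brochure as a separate step, after causality.
- **Protocol 11.2, 11.3 and 11.5.5:** reconcile these sections. Changing the grades changes which events meet the suspension wording, so the sponsor must decide deliberately how the two relate. No particular rule is proposed here.
- **SAP 4.4:** present related AEs for weeks 26 to 39 separately from the 16-02 period, so that events graded under different wording are not pooled unseen.

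The cost is protocol and eCRF-guideline wording plus one further table by period. Somewhat more events will be rated possibly related, and the grades will not be identical to those used in 16-02 up to week 26. If that loss of comparability is unacceptable, a fallback is a system-organ-class and preferred-term table of all AEs regardless of relationship. It would restore the missing display without touching the scale, but it would leave the conflict between 11.2 and 11.3 in place.

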11.4 Severity

The severity of AEs will be assessed according to the following definitions:

Mild: The Adverse Event is noticeable to the subject, but does not interfere with routine activity.

Moderate: The Adverse Event interferes with routine activity but responds to symptomatic therapy or rest.

Severe: The Adverse Event significantly limits the subject's ability to perform routine activities despite symptomatic therapy.

11.5 Reporting

11.5.1 Adverse Events

All AEs that occur after signing the ICF will be recorded. At each visit during the trial, AEs that have occurred since the previous visit must be recorded. All subjects will be questioned and evaluated for

AEs or complications associated with the procedure. Complications of the injection include, but are not necessarily limited to: pain, swelling and/or inflammation at the injection site. The Investigator will determine the severity and relationship of each event, as defined above.

AEs observed during the course of this study, regardless of severity or relationship to the injection will be recorded on the appropriate eCRF. Each reported complication/AE will also include the duration, action taken to address the AE, and the resolution status (e.g. ongoing, resolved). These subjects will continue to be evaluated for safety and efficacy at all scheduled follow-up points.

The sponsor must report the results of an evaluation of an unanticipated adverse device effect (UADE) to relevant regulatory agencies and all reviewing ECs and investigators within timelines required by the regulatory agencies.

